10. Tumor assessment	Radiological (PET-CT + CT*) and clinical tumor assessment.  In the case a patient continues in treatment beyond Cycle 6, CT scans may be used every four months (+ 2 weeks) for the first two years and every six months (+ 2 weeks) thereafter, but any subsequent improvement in response should be confirmed by PET-CT*.  Disease progression at any time during the study should be confirmed by imaging (if the physical condition of the patient permits).	One to two weeks after last dose of Cycle 3 and at least 4 weeks (but no more than 8 weeks) after last dose of Cycle 6 (or earlier in the event of treatment discontinuation for whatever reason). Cycle 4 can be started without waiting for the results of the Cycle 3 tumor assessment. No radiological assessment is necessary in the event of discontinuation due to any reason other than PD during or after Cycle 4 if the Cycle 3 radiological assessment has been performed correctly.
11. Concomitant medications	All concomitant therapies taken by the patient (including any not prescribed by the Investigator) should be documented with indication from two weeks prior to starting study treatment.	Throughout the on-treatment period.
12. Adverse events **	As per NCI-CTCAE v.4.	Throughout the on-treatment period.

\* When PET-CT is performed it must be in combination with diagnostic quality CT with intravenous contrast (except medically contraindicated). Two alternatives are allowed: Hybrid PET CT scanners may be used to acquire diagnostic quality CT which includes intravenous contrast OR PET CT without intravenous contrast and diagnostic quality CT images with intravenous contrast using a standalone CT scanner must be performed.

\*\* Clinical assessment of the patient's signs and symptoms (if any and including nurses' assessment and patient-reported issues) should continue on an ongoing basis throughout the study and be reported at least every cycle (unless relevant enough to program an unscheduled visit or the criteria for seriousness are reached and an SAE report is required). Assessments for a particular visit do not need to all take place on the same day but should all be within the planned time window. Physical examination and laboratory assessments, for example, can be performed more frequently during the study if clinically required.

Permitted windows for assessments

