## **9.2 STATISTICAL ANALYSIS**

### **9.2.1 Efficacy**

For ORR and CR rate, the exact binomial estimator and its 95% confidence interval (CI) will be used. The test statistic for stopping boundaries and final analysis will be calculated using observed results and normal distribution.

Time-to-event variables (DoR, PFS and OS) will be analyzed according to the Kaplan-Meier method. Time to event endpoints will be used as exploratory endpoints.

Intra-patient PFS/TTP ratio will be categorized and analyzed as a dichotomous variable. Clinical benefit will be defined in the event of > 33% longer PFS with the experimental treatment vs. TTP with the immediate prior chemotherapy in R/R setting (ratio >1.33) ([66](#), [67](#)).

Frequency tables will be prepared for categorical variables, whereas continuous variables will be described by means of summary tables that will include the median, mean, standard deviation, minimum, and maximum of each variable.

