Progression-free survival (PFS) is defined as the time from the date of first administration to the date of documented progressive disease (PD) or death (regardless of the cause of death). If the patient receives further antitumor therapy (including stem cell transplant) before, PFS will be censored on the date of the last disease assessment prior to the administration of this antitumor therapy. If the patient is lost to follow-up for the assessment of progression the PFS will be censored at the date of last valid tumor assessment. If the patient does not received any drug infusion, he/she will be censored at time zero. Both, independent central review and investigator assessments, will be used for the determination of PFS.

Progression-free survival at 6/12 months (PFS6/PFS12), defined as the Kaplan-Meier estimate of the percentage of patients who are progression-free at six/twelve months after first administration; both independent central review and investigator assessment will be used for the determination of PFS.

Within-patient PFS/TTP, defined as the ratio of the PFS achieved with the experimental treatment versus prior last TTP. Intra-patient PFS/TTP ratio will be categorized and analyzed as a dichotomous variable. Clinical benefit will be defined if a >33% longer PFS/TTP with the experimental treatment vs. the TTP with the immediate prior chemotherapy (ratio >1.33) is achieved.

Overall survival (OS), defined as the time from the date of first administration to the date of death (of any cause) or last patient contact.

Overall survival at 6/12 months (OS6/OS12), defined as the Kaplan-Meier estimate of the percentage of patients who are alive at six/twelve months after first administration.

Treatment safety [AEs, serious adverse events (SAEs) and laboratory abnormalities] graded according to the NCI-CTCAE, v. 4. Dose reductions, skipped doses or dose delays required due to treatment-related AEs, and reasons for treatment discontinuations will be analyzed.

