6.2.2 Secondary analyses

Time to event endpoints will be used in an exploratory way.

Binomial estimates with exact 95% CIs will be calculated for the analysis of **complete remission rate** in the "Per Protocol Patients", "All Evaluable Patients" and "All Treated Patients" analysis sets by independent review and investigator assessment.

Duration of response will be analyzed according to the Kaplan-Meier method in "All Responder Patients" analysis set by independent review and investigator assessment.

Time to response is defined as the time, in months, from the date of first drug administration to the first documentation of response method in "All Responder Patients" analysis set by independent review and investigator assessment.

PFS analysis will be performed in "Per Protocol Patients", "All Evaluable Patients" and "All Treated Patients" analysis sets according to the Kaplan-Meier method by independent review and investigator assessment. The concordance between the IRC and investigator evaluation of response and PFS will be shown using counts and percentages.

OS analysis will be performed in “Per Protocol Patients”, “All Evaluable Patients” and “All Treated Patients” analysis sets according to the Kaplan-Meier.

Univariate evaluation of the influence of different prognostic factors on the main efficacy endpoints will be performed. If appropriate, univariate analyses will include prognostic factors/covariates widely reported and recognized by hematologist such as: sex, age at diagnosis, baseline ECOG, Body Surface Area, Ann arbor, extranodal disease, bone marrow involvement, B symptoms, baseline LDH xULN, bulky lesion, IPI, PIT, PIAI, Relapse or refractory, number of prior lines of treatment, previous SCT or time from last PD before inclusion. Further covariates could be included upon hematologist criteria.

Cox proportional hazard models for PFS and OS, and logistic regression models for ORR will include the prognostic factors specified for the univariate analysis. More relevant and explanatory covariates from the univariate analysis will be included in the multivariate analyses (p-value < 0.10). Prognostic factors with more than 10% missing values will be excluded in the multivariate analyses.

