Table 11.3.2.21 Time to response (Investigator assessment and “All Responder Patients” population)

N	X
Median	X
Minimum	X
Maximum	X.X

Table 11.3.2.22 PFS (Independent Review assessment and “Per Protocol Patients” population)

N	X
Events	X
Censored	X
Median PFS	X.X
PFS at 6 months	X.X
PFS at 12 months	X.X

Kaplan-Meier plot will be also shown (Figure 11.3.2.22)

Table 11.3.2.23 PFS (Independent Review assessment and “All Evaluable Patients” population)

N	X
Events	X
Censored	X
Median PFS	X.X
PFS at 6 months	X.X
PFS at 12 months	X.X

Kaplan-Meier plot will be also shown (Figure 11.3.2.23)

Table 11.3.2.24 PFS (Independent Review assessment and “All Treated Patients” population)

N	X
Events	X
Censored	X
Median PFS	X.X
PFS at 6 months	X.X
PFS at 12 months	X.X

Kaplan-Meier plot will be also shown (Figure 11.3.2.24)

Table 11.3.2.25 PFS (Investigator assessment and “Per Protocol Patients” population)

N	X
Events	X
Censored	X
Median PFS	X.X
PFS at 6 months	X.X
PFS at 12 months	X.X

Kaplan-Meier plot will be also shown (Figure 11.3.2.25)

Table 11.3.2.26 PFS (Investigator assessment and “All Evaluable Patients” population)

N	X
Events	X
Censored	X
Median PFS	X.X
PFS at 6 months	X.X
PFS at 12 months	X.X

Kaplan-Meier plot will be also shown (Figure 11.3.2.26)

Table 11.3.2.27 PFS (Investigator assessment and “All Treated Patients” population)

N	X
Events	X
Censored	X
Median PFS	X.X
PFS at 6 months	X.X
PFS at 12 months	X.X

Kaplan-Meier plot will be also shown (Figure 11.3.2.27)

Table 11.3.2.28 PFS – Concordance between Independent Review assessment and Investigator assessment (“Per Protocol Patients” population)

	N	%
Event by investigator		
Agreement on event		
Same date		
Later date		
Earlier date		
Censored by investigator		
Agreement on censoring		
Same date		
Different date		
Agreement on status		
Agreement on status and date		

Table 11.3.2.29 Intra-patient PFS/TTP ratio (Independent Review assessment and “Per Protocol Patients” population)

Ratio		
	N	%
≤1.33	X	X.X
>1.33		

Table 11.3.2.30 Intra-patient PFS/TTP ratio (Independent Review assessment and “All Evaluable Patients” population)

Ratio		
	N	%
≤1.33	X	X.X
>1.33		

Table 11.3.2.31 Intra-patient PFS/TTP ratio (Independent Review assessment and “All Treated Patients” population)

Ratio		
	N	%
≤1.33	X	X.X
>1.33		

Table 11.3.2.32 Intra-patient PFS/TTP ratio estimates (Independent Review assessment and “Per Protocol Patients” population)

	Proportion	Lower 95% limit	Upper 95% limit
Ratio	X.X	X.X	X.X

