Binomial exact estimator and 95% confidence interval

Table 11.3.2.33 Intra-patient PFS/TTP ratio estimates (Independent Review assessment and “All Evaluable Patients” population)

	Proportion	Lower 95% limit	Upper 95% limit
Ratio	X.X	X.X	X.X

Binomial exact estimator and 95% confidence interval

Table 11.3.2.34 Intra-patient PFS/TTP ratio estimates (Independent Review assessment and “All Treated Patients” population)

	Proportion	Lower 95% limit	Upper 95% limit
Ratio	X.X	X.X	X.X

Binomial exact estimator and 95% confidence interval

Table 11.3.2.35 Intra-patient PFS/TTP ratio (Investigator assessment and “Per Protocol Patients” population)

Ratio		
	N	%
≤1.33	X	X.X
>1.33		

Table 11.3.2.36 Intra-patient PFS/TTP ratio (Investigator assessment and “All Evaluable Patients” population)

Ratio		
	N	%
≤1.33	X	X.X
>1.33		

Table 11.3.2.37 Intra-patient PFS/TTP ratio (Investigator assessment and “All Treated Patients” population)

Ratio		
	N	%
≤1.33	X	X.X
>1.33		

Table 11.3.2.38 Intra-patient PFS/TTP ratio estimates (Investigator assessment and “Per Protocol Patients” population)

	Proportion	Lower 95% limit	Upper 95% limit
Ratio	X.X	X.X	X.X

Binomial exact estimator and 95% confidence interval

Table 11.3.2.39 Intra-patient PFS/TTP ratio estimates (Investigator assessment and “All Evaluable Patients” population)

	Proportion	Lower 95% limit	Upper 95% limit
Ratio	X.X	X.X	X.X

Binomial exact estimator and 95% confidence interval

Table 11.3.2.40 Intra-patient PFS/TTP ratio estimates (Investigator assessment and “All Treated Patients” population)

	Proportion	Lower 95% limit	Upper 95% limit
Ratio	X.X	X.X	X.X

Binomial exact estimator and 95% confidence interval

Table 11.3.2.41 OS (“Per Protocol Patients” population)

N	X
Events	X
Censored	X
Median OS	X.X
OS at 6 months	X.X
OS at 12 months	X.X

Kaplan-Meier plot will be also shown (Figure 11.3.2.41).

Table 11.3.2.42 OS (“All Evaluable Patients” population)

N	X
Events	X
Censored	X
Median OS	X.X
OS at 6 months	X.X
OS at 12 months	X.X

Kaplan-Meier plot will be also shown (Figure 11.3.2.42).

Table 11.3.2.43 OS (“All Treated Patients” population)

N	X
Events	X
Censored	X
Median OS	X.X
OS at 6 months	X.X
OS at 12 months	X.X

Kaplan-Meier plot will be also shown (Figure 11.3.2.43).

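### A PFS/TTP ratio above 1.33 is called clinical benefit, but about 43% of patients would exceed it by chance with no drug effect, and the tables give no such reference

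*SAP*

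**What the plan says.** SAP 6.1.2 lists the within-patient measure among the secondary endpoints, "defined as the ratio of the PFS achieved with the experimental treatment versus prior last TTP". It continues: "Intra-patient PFS/TTP ratio will be categorized and analyzed as a dichotomous variable". The upper category is then named: "Clinical benefit will be defined if a >33% longer PFS/TTP with the experimental treatment". Protocol 9.2.1 carries the same label: "Clinical benefit will be defined in the event of > 33% longer PFS with the experimental treatment".

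SAP 11.3.2 gives twelve displays, Tables 11.3.2.29 to 11.3.2.40, for three populations and two assessors. Six are counts with two rows, at or below 1.33 and above 1.33. Six give the proportion, footnoted "Binomial exact estimator and 95% confidence interval". No reference proportion, success threshold or test is attached to any of them.

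On the status of these endpoints, SAP 6.2.2 says: "Time to event endpoints will be used in an exploratory way".

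Scheduled trial scans are set in Protocol 5.8, Table 5, with the second one tied to the sixth cycle: "One to two weeks after last dose of Cycle 3 and at least 4 weeks (but no more than 8 weeks) after last dose of". Protocol 3 adds CT every four months for two years. Scans are also made at suspected clinical progression. Prior TTP comes from the treatment history where it is available (Protocol 5.4, Table 4), and neither document has a rule for how that earlier progression was dated.

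**The concern.** Two progression times from the same patient differ by more than a third very often, whatever the drug does. A rule that fires whenever the second exceeds the first by a third will therefore label many patients as benefiting when the drug is no better than the therapy they last failed. A single-arm trial has no control group to show how many. The tables also hide the one internal comparison available: patients whose ratio is a third worse are pooled with those whose ratio is near 1.

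The risk is a clinical study report that states clinical benefit in some 40% of patients, with an interval around it, when that figure is what chance alone would give.

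**Working it through.** **Inputs from the documents.** The cut-off is 1.33 and the planned number is 60 patients (SAP 5). Dosing is on Days 1, 8 and 15 of 28-day cycles (Protocol 7.2). Median TTP/PFS was 1.6 months in the earlier plitidepsin PTCL cohort (Protocol Table 1), and median PFS was 3.6 months in the bendamustine PTCL trial (Protocol 1.1.5).

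**Assumptions, not in the documents.** Exponential times, within-patient correlation 0 to 0.8, a longest median of 6 months, the share of progressions that stay silent until a scheduled scan, and how prior TTP was dated.

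**Plan's own figure.** The plan gives none for this endpoint. The exact-interval method was checked on the ORR example: 19/60 = 31.7%, CI 20.3–45.0%, as the SAP states.

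**Step 1: no-effect proportion.** For independent exponentials with hazards h₁ (trial) and h₀ (prior), P(ratio > c) = h₀/(h₀ + c·h₁).
- Equal hazards: 1/(1 + 1.33) = 42.9%. In 60 patients that is 25.8, so about 26; the exact CI for 26/60 is 31–57%.
- Equal medians with correlated times (simulated): 40% at correlation 0.5 and 34% at 0.8.
- Hazard 1.5 times higher on the later line: 1/(1 + 1.33 × 1.5) = 33%.
- Hazard halved by the drug: 1/(1 + 1.33 × 0.5) = 60%.

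**Step 2: the mirror category.** If the two times are exchangeable, P(ratio > 1.33) = P(ratio < 1/1.33), and 1/1.33 is 0.75 to two decimals. For independent exponentials P(ratio < 0.75) = 0.75/1.75 = 42.9%, the same as above 1.33.

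**Step 3: scan dates.** The last Cycle 3 dose is on day 2 × 28 + 15 = 71. Adding 7–14 days puts the first scan on day 78–85, which is 77–84 days after the first dose. The last Cycle 6 dose is on day 5 × 28 + 15 = 155. Adding 28–56 days puts the second scan on day 183–211.

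**Step 4: effect of dating.** No drug effect, correlation 0; silent trial progressions are moved to the next scheduled scan. The entries are the proportions above 1.33.

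| Median | Prior TTP exact, all silent | Prior TTP exact, half silent | Both on the trial schedule, all silent |
|---|---|---|---|
| 1.6 months | 67–69% | 55–56% | 22–24% |
| 3.6 months | 55–56% | 49–50% | 35–36% |
| 6 months | 51–52% | 47% | 39–40% |

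The shift is upward if only the trial time is rounded to sparse scans, and downward if both are.

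**Step 5: does the mirror comparison survive unequal dating?** With both times on the same schedule it does: the two proportions stay equal (about 24% each at a 49-day median). With prior TTP exact and every trial progression silent it does not: 68% against 16% at 49 days, using scans at 80 and 196 days and then every 122 days. Dating scan-detected progression at the interval midpoint narrows that to 49% against 34%.

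**Step 6: a sign test on the two outer categories.** For n = 60, one-sided 0.025, the false-positive rate is 1.9% when the times are exchangeable. Over medians of 49–180 days with prior TTP exact, it is about 10–55% if half of the progressions are silent and 32–99.7% if all are. With midpoint dating the figure for the 49-day, all-silent case is still 22%.

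**The case against.** The strongest reply is that nothing rests on this ratio. Time-to-event endpoints are exploratory, the ratio has no test or threshold, and the trial's conclusion comes from 19 responders in 60. The 1.33 cut-off is supported by two cited references. All of that stands, and it limits the weight of the point. It does not supply the missing reference, and the label appears in both documents.

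A reader might infer that the sparse trial scans bias the proportion upward, to 47–69%. The documents do not support that. It needs exactly dated prior TTP and at least half of the trial progressions silent until a scheduled scan, and neither is stated. Unscheduled scans at suspected progression, earlier scans at discontinuation, and death as a PFS event all reduce silence. If prior TTP was read on an equally sparse schedule, the proportion falls below 43%. The direction is unknown.

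A reader might also infer that the endpoint cannot separate benefit from none. That is too strong. If a 43% reference were defensible, 34 of 60 would put the exact lower limit above it, with 75% power at a true 60% (a doubled median). What is missing is the benchmark. The choice of benchmark matters, though: with a reference of 57%, 43 of 60 would be needed and power at 60% would be 4%.

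**Conclusion.** The point holds as a reporting defect in an exploratory secondary endpoint. With no drug effect, about 43% of patients exceed 1.33 under equal, independent exponential times, 40% at correlation 0.5 and 34% at 0.8. Unequal dating could take this to roughly 22–69% for medians of 1.6–6 months, in a direction that the documents do not settle. The planned proportion and interval, shown without a reference, therefore cannot be read as evidence of benefit.

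The interval offers no false precision: at 26/60 it is 26 points wide. The ORR decision is untouched. The change is worth making because it is nearly free, but the trial does not depend on it.

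**What to change.** - In Tables 11.3.2.29–31 and 35–37, keep the 1.33 cut-off and split the lower row into below 0.75 and 0.75 to 1.33.
- In Tables 11.3.2.32–34 and 38–40, give the proportion above 1.33 beside the proportion below 0.75, with their difference and its CI. Describe the comparison as exploratory and valid only if PFS and prior TTP are exchangeable.
- State the no-effect reference of about 43% with its assumptions.
- In SAP 6.1.2 and Protocol 9.2.1, name the category by its value (ratio above 1.33) and say that the bare proportion is not interpreted as clinical benefit.
- Add one sensitivity analysis that dates PD first seen at a scheduled scan at the midpoint between that scan and the previous assessment. It adjusts the trial time only, so it shows sensitivity and is not a full correction.
- Do not award the benefit label by a sign test of the outer categories, since unequal scan dating inflates its false-positive rate (Step 6).

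Cost: one extra row in existing tables, one difference with its CI, one sensitivity run, and a small wording change in the protocol as well as the SAP. No new data are needed. The apparent benefit figure will look less favourable.

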6.2 Efficacy analysis methods

6.2.1 Primary endpoint

For the evaluation of the main primary endpoint, **ORR**, the "Per Protocol Patients" population, the data from the Independent Review will be used. Binomial estimates with exact 95% CIs will be calculated for the analysis of response rate. A supportive analysis will be also done in the "All Evaluable Patients" and "All Treated Patients" populations and by investigator assessment as a secondary analysis.

6.2.2 Secondary analyses

Time to event endpoints will be used in an exploratory way.

Binomial estimates with exact 95% CIs will be calculated for the analysis of **complete remission rate** in the "Per Protocol Patients", "All Evaluable Patients" and "All Treated Patients" analysis sets by independent review and investigator assessment.

Duration of response will be analyzed according to the Kaplan-Meier method in "All Responder Patients" analysis set by independent review and investigator assessment.

Time to response is defined as the time, in months, from the date of first drug administration to the first documentation of response method in "All Responder Patients" analysis set by independent review and investigator assessment.

PFS analysis will be performed in "Per Protocol Patients", "All Evaluable Patients" and "All Treated Patients" analysis sets according to the Kaplan-Meier method by independent review and investigator assessment. The concordance between the IRC and investigator evaluation of response and PFS will be shown using counts and percentages.

OS analysis will be performed in “Per Protocol Patients”, “All Evaluable Patients” and “All Treated Patients” analysis sets according to the Kaplan-Meier.

Univariate evaluation of the influence of different prognostic factors on the main efficacy endpoints will be performed. If appropriate, univariate analyses will include prognostic factors/covariates widely reported and recognized by hematologist such as: sex, age at diagnosis, baseline ECOG, Body Surface Area, Ann arbor, extranodal disease, bone marrow involvement, B symptoms, baseline LDH xULN, bulky lesion, IPI, PIT, PIAI, Relapse or refractory, number of prior lines of treatment, previous SCT or time from last PD before inclusion. Further covariates could be included upon hematologist criteria.

Cox proportional hazard models for PFS and OS, and logistic regression models for ORR will include the prognostic factors specified for the univariate analysis. More relevant and explanatory covariates from the univariate analysis will be included in the multivariate analyses (p-value < 0.10). Prognostic factors with more than 10% missing values will be excluded in the multivariate analyses.

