8.7 Subgroup analyses

No specific subgroup analysis is planned for efficacy. However, the influence of prognostic factors on the efficacy endpoints will be studied in the multivariate analysis.

No formal statistical allowance will be made for multiple subgroup investigations, but any apparent subgroup interactions will be interpreted appropriately in a cautious way.

Analysis of safety profile by age, gender, race and body mass index (BMI) will be provided as specified in section 12.7.

Handling of multicenter data

Not applicable.

Handling of multiple comparisons

No formal statistical allowance will be made for multiple comparisons, therefore any apparent subgroup analysis will be interpreted appropriately in a cautious way.

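### The SAP screens 17 or more prognostic covariates at p<0.10 and lets IPI, PIT and PIAI enter a model with their own components; a short pre-named set would be more readable and less prone to false entries

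*SAP*

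**What the plan says.** SAP 6.2.2 gives its candidates as examples. Ten come first: "sex, age at diagnosis, baseline ECOG, Body Surface Area, Ann arbor, extranodal disease, bone marrow involvement, B symptoms, baseline LDH xULN, bulky lesion". Seven follow: "IPI, PIT, PIAI, Relapse or refractory, number of prior lines of treatment, previous SCT or time from last PD before inclusion". That makes 17, and the list stays open: "Further covariates could be included upon hematologist criteria".

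Two sentences then govern model content. One says that Cox models for PFS and OS and "logistic regression models for ORR will include the prognostic factors specified for the univariate analysis". The next restricts entry: "More relevant and explanatory covariates from the univariate analysis will be included in the multivariate analyses (p-value < 0.10". The only other stated exclusion is "Prognostic factors with more than 10% missing values will be excluded in the multivariate analyses". There is no rule on overlap between covariates, number of events per covariate, retention in the final model, shrinkage or validation.

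SAP 8.7 plans no specific efficacy subgroup analysis and says instead that "the influence of prognostic factors on the efficacy endpoints will be studied in the multivariate analysis". It makes no allowance for multiple comparisons and asks for caution with subgroup findings. SAP 6.2.2 calls the time-to-event endpoints exploratory, but no such label is attached to the ORR logistic models. SAP 11.3.4 plans 15 multivariable tables: six for PFS, six for ORR and three for OS.

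**The concern.** There are two separate problems.

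**Screening.** Testing 17 or more factors one by one at p<0.10 and carrying the survivors into a model lets chance associations through. For ORR the information is limited by the number of responders, which is small in a 60-patient trial. The p-values and confidence limits from the selected model take no account of the selection.

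**Overlap.** An index and its parts carry the same information, so when one is prognostic the others tend to pass the screen with it. The index coefficient is then the effect of the index with its own components held fixed, which answers no clinical question.

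At stake are the reported prognostic factors, which readers may carry into the design of later studies. The decision on plitidepsin activity is not at stake.

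**Working it through.** **1. The plan's own figure.** SAP section 5 sets success at 19 responders of 60. 19/60 = 31.7%, and the exact 95% interval recomputes to 20.3%–45.0%, as stated.

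**2. Responders available to the ORR models.** At P0 = 0.208: 60 × 0.208 = 12.5. At the success boundary: 19. At Pa = 0.41: 60 × 0.41 = 24.6. Divided by 17 candidates, this is 0.7, 1.1 and 1.4 responders per candidate.

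**3. Overlap.** Index components are taken from footnote 2 of the protocol's Schedule of Assessments.

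| Index | Components | Also listed singly in SAP 6.2.2 |
|---|---|---|
| IPI | age, stage, LDH, extranodal sites, performance status | 5 of 5 |
| PIT | age, performance status, LDH, marrow | 4 of 4 |
| PIAI | age, performance status, extranodal sites, B symptoms, platelets | 4 of 5 (not platelets) |

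**4. Screen with no true effect, 17 independent tests.** Expected false entries: 17 × 0.10 = 1.7. P(at least one) = 1 − 0.9^17 = 83.3%. P(at least two) = 1 − 0.9^17 − 17 × 0.1 × 0.9^16 = 51.8%.

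**5. Simulated screen followed by the logistic model.** No true effect, n = 60, 3,000 runs per row, Monte Carlo standard error at most 0.9 percentage points. In the overlapping rows the three indices are built from their components.

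| Covariates | Responders | Mean entries | At least one entry | At least one p<0.05 in the ORR model |
|---|---|---|---|---|
| Independent | 12 | 1.4 | 76% | 40% |
| Independent | 19 | 1.7 | 82% | 48% |
| Independent | 24 | 1.7 | 84% | 54% |
| Overlapping | 12 | 1.4 | 73% | 35% |
| Overlapping | 19 | 1.6 | 77% | 37% |
| Overlapping | 24 | 1.7 | 78% | 40% |

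A separate simulation with overlap and 19 responders gave 1.5 entries, 76% and 39%. An index entered together with one of its components in 16% of null runs, and in 64% of runs when IPI was given a real effect.

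**6. Adding PFS and OS.** 600 runs with overlapping covariates. Assumed: median PFS 8 months in responders and 2 months in the rest; OS equal to PFS plus an exponential time with median 6 months; censoring uniform over 12 to 48 months. This gives about 58 PFS and 51 OS events. The chance of at least one false p<0.05 was 45–47% in the PFS model and 45–48% in the OS model. Across one ORR, one PFS and one OS model it was 79–81%.

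**7. A short pre-named set, no screen, 19 responders.** The chance of at least one false p<0.05 among k independent covariates is 1 − 0.95^k.

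| k | Responders per covariate | Chance |
|---|---|---|
| 2 | 9.5 | 9.8% |
| 3 | 6.3 | 14.3% |
| 4 | 4.8 | 18.5% |

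**The case against.** The strongest reply is that this is secondary output that nobody will use for a decision, and that the SAP already signals caution. Much of that stands. The primary ORR analysis, the 19-of-60 rule and the futility rules are untouched. The time-to-event endpoints are labelled exploratory, and SAP 8.7 is open about making no multiplicity adjustment. What the reply leaves uncovered is the ORR models, which carry no exploratory label, and the overlap, which a caution about multiplicity does not address.

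A reader might also infer several things that the documents do not support:

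- **That every model is short of events.** Only the six ORR tables depend on the responder count. The nine Cox tables depend on PFS or OS events.
- **That all 17 factors are fitted together.** The p<0.10 sentence implies a smaller model: at 1.6 entries and 19 responders, about 19/1.6 = 12 responders per fitted covariate. The preceding sentence can be read as putting everything in, so the two need reconciling.
- **That overlap raises the false-positive rate.** At 19 responders the rate was 37% with overlap and 48% without. Overlap damages interpretation, not this error rate.
- **That this is the only planned look at who benefits.** The univariate evaluation in 6.2.2, the biomarker analyses under 8.5 and the listing of patients with clinical benefit in 11.3.6 are also planned. In a single-arm trial these models describe prognosis, not treatment benefit.
- **That every endpoint is analysed under two assessors.** OS has no assessor split.

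Finally, the indices may not be built from exactly the listed variables. SAP 11.1.3 tabulates each index both at diagnosis and at current disease, and 6.2.2 does not say which is used. ECOG and LDH are baseline values, while age is age at diagnosis and SAP 11.1.3 tabulates stage and extranodal disease at diagnosis. So either version would share some components with the list. This is a further gap, not a defence.

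**Conclusion.** The point holds as a matter of analysis quality. With no true effect, the planned screen admits at least one factor with probability about 76–83% at 19 responders, or 73–84% over 12 to 24. One ORR model shows at least one p<0.05 with probability about 35–54%. It would therefore be too strong to call a spurious factor likely in any one ORR model. That description fits passing the screen and, at about 80% under the assumed survival times, the three endpoints taken together.

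The count of 17, the open list, the threshold, the overlap and the responder range come from the documents. The simulated figures rest on assumed prevalences, correlations and survival times. The 64% co-entry figure also depends on the assumed size of the IPI effect, so it shows the direction of the problem and is not a forecast.

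**What to change.** In SAP 6.2.2:

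1. State that IPI, PIT or PIAI will not be entered in the same model as any of its components.
2. State which version of each index is used, at diagnosis or at current disease.
3. Replace the p<0.10 screen with a short covariate set named before the data are seen and sized to the expected events. Use this to reconcile the two sentences on model content. The exact cap is a judgement; step 7 of the working shows what two to four covariates mean for ORR. Penalised logistic regression, such as Firth's method, is one option for ORR. Say what happens if a named covariate breaches the 10% missing-data rule.
4. Report all other factors as univariate estimates with confidence intervals. SAP 11.3.4 has shells for the multivariable results only, so a univariate shell would be added.
5. Label all of these models, including those for ORR, exploratory.

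The cost is SAP wording and a table shell; no data, visits or sample size change. The downside is that fewer factors are adjusted for jointly in an exploratory analysis. This is a cheap improvement.
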